Exclusion criteria will be active participation in a physical therapy program with the goal of improving functional mobility, missing six or more of the ballet classes offered during the 10-week period, receiving dance training in the past, not being independent with ADLs, using a walking aide, or diagnosis of cardiovascular or neurological disease. However, participants will not be excluded if they have a pacemaker if they are also cleared by a physician as a 'no restrictions' status for physical activity as indicated by the required intake form. Additionally, we will recruit a control group of adults ages 55 and up that will not participate in the dance class. As with the experimental group, control group participants must be independent with ADLs, require no walking aides, and be free from cardiovascular or neurological disease. Exclusion criteria for the control group will be participation in a physical therapy program with the goal of improving functional mobility, receiving dance training in the past, not being independent with ADLs, using a walking aide, or diagnosis of cardiovascular or neurological disease. The control and treatment groups are determined by the individuals themselves based on their desire to participate in the ballet classes.

B. How many participants do you plan to have in your study?

Each semester, we aim to recruit a convenience sample of up to 20 people for the control group and 20 people for the experimental group. We will cap the class at 20 each semester to assure a safe and appropriate ratio of students in the classroom. We aim to have one Skidmore dance student act as the lead teacher and be present at every ballet class, at least 1-2 additional Skidmore students assistant-teaching each class, and up to 20 individuals participating in the dance classes. Participants will be

responsible for finding transportation to campus and will be greeted by at least one participating Skidmore students at Dance Center entrance.

Participants may opt to leave the ballet classes and the study at any time. Participants who opt to withdraw from the study will not be asked to participate in the postural stability post-testing procedures.

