“Your decision to join this program or not join this program will not affect your relationship with Skidmore College in any way. If you decide that you do want to join the program, you can stop at any time. You can also choose not to participate at all or you can choose not to answer certain questions or do certain activities that we ask you to do. Also, you can stop participating in the program at any time without penalty or being in trouble in any way.”

D. Will the participants be compensated for participating? If so, describe:

Participants will not be compensated for their participation.

11. Procedures:

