11.1 Beginning Ballet Class Information

One-hour ballet classes will be held twice per week in one of the two dance studios or in the dance theater at Skidmore College. [name] '20 will serve as the lead teacher for each dance class from February 4th-April 26th. Other Skidmore students may serve as lead teacher in future semesters as determined by the PI and/or [name]. Each week the participants will partake in 120 minutes of ballet dance training, starting with warm-up exercises at the barre and then working towards learning combinations in the center. Participants may take short breaks to get a drink or use the bathroom as they need. Chairs will be set up in the dance studio or dance theater so individuals can rest

or take a break if they wish. They will learn the basic positions and combinations used in ballet, including: Plié, Tendu, Degagé, Rond de Jambe, Frappé, Chassé, Sauté, Pas de Bourrée, Glissade, and Révérence. Additional ballet movements and patterns may be employed as well. If a participant chooses not to dance for the full duration of a given class period, an assistant teacher may assist them out of the studio to wait comfortably in the lobby of the dance center, dance gym or sports center until the class ends and their transportation arrives if needed. They may also rejoin the class at any time, should they choose. Attendance will be taken at the start of each class to ensure that participants do not miss six or more classes in line with our exclusion criteria. Attendance will be documented in a password-protected electronic file through the participants' number IDs alongside the initials of their first and last name to maintain anonymity of the attendance document. Only [name], [name], and the lead teacher will have access to the attendance roster each semester.

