11.3 Data Analysis

Five measures of postural stability were examined in this study: the area the CoP traveled through during each 30-second trial, the CoP displacement in the x- and y-planes during each trial, and the absolute value of the average speed of the CoP in the x- and y-planes through each trial. Non-parametric Wilcoxon signed ranks tests were used to compare these values at baseline and post-testing within each group, while non-parametric Mann Whitney U tests were used to compare the delta (post minus pre) values between groups for EO and EC trials.

12. Consent:

Participants will sign an Informed Consent must prior to beginning of any testing. Please see attached informed consent for details.

13. Risks and Debriefing:

The postural stability data collection offers minimal risk to participants. Fatigue and falls have been shown to be minimal in prior research (see background information on postural stability references) in older adults. To ensure no risk to participants, participants will repeatedly be reminded they may rest or stop at any moment, without penalty of any kind. As well, one 'spotter' will be present during all data collection trials to assist participants should they lose their balance.

The dance movements performed in the intervention sessions carry a minimal risk of injury. Ballet movements presented in the class will likely be outside of typical movement patterns and therefore hold some inherent risk, including slips, falls and muscle strains and sprains. To combat the likelihood of injury during the class, participants will be thoroughly instructed on the movement, technique, and expectations for each combination. The ballet class will be gentle with little to no aerobic activities, making this appropriate for all participants meeting our inclusion criteria. Additionally, while the class will be primarily instructed by the lead teacher, additional Skidmore students will be present to help decrease the risk of injury during the dance class. This way, each participant has additional support throughout the class time as needed.

If a serious injury occurs, the Skidmore Campus Safety will be called and/or 911 depending on the severity of the injury. If an injury occurs during testing off-campus, 911 will be called to appropriately treat the participant for any injury sustained.

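### Stopping the ballet classes is not separated from withdrawing from the study, so dancers who quit class will probably have no post-test, on top of a dancer-only attendance exclusion

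*Combined protocol and SAP*

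**What the plan says.** - Section 10.B, on leaving: "Participants may opt to leave the ballet classes and the study at any time". The next sentence is: "Participants who opt to withdraw from the study will not be asked to participate in the postural stability post-testing procedures". It applies to participants in general and names only the balance tests.
- Section 10.C, standard email wording: "you can choose not to answer certain questions or do certain activities that we ask you to do". So partial participation is offered, but no section says how a dancer who stops class and stays in the study is followed up.
- Section 10.A lists among the exclusions for dancers "missing six or more of the ballet classes offered during the 10-week period". Section 11.1 enforces the same limit through the class register, in a sentence that goes on to cite that list: "Attendance will be taken at the start of each class to ensure that participants do not miss six or more classes in line with our". For controls, the exclusions contain no attendance rule, and section 10.A describes the comparison arm thus: "we will recruit a control group of adults ages 55 and up that will not participate in the dance class".
- Section 11.3: Wilcoxon signed ranks tests are "used to compare these values at baseline and post-testing within each group", and Mann-Whitney tests compare post-minus-pre change between groups. No analysis population and no method for missing post-tests is given.
- Section 11.1 places the SF-36 at pre- and post-testing. Section 11.3 describes no SF-36 analysis.

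**The concern.** A dancer may want to stop dancing without wishing to leave the research. Section 13 itself anticipates slips, falls, strains and sprains in class, and frustration or discouragement with the movements. Some of these are plausibly linked to balance. Staff following section 10.B have no instruction to invite that person back, so the post-test is likely to be lost.

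The dancers analysed would then be those who tolerated the class, compared with controls who had no class to tolerate. If the dancers lost were doing worse on sway, both the within-dancer test and the between-group comparison of change would lean toward the hypothesis. A post-test that was not taken cannot be recovered after the semester ends.

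**Working it through.** The plan states no power, significance level, standard deviation or dropout rate, so there is no planned figure to reproduce. What follows is illustrative.

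**Inputs from the plan.** Up to 20 dancers and 20 controls per semester (10.B); two classes a week (11.1); a programme of 10 to 12 weeks (10.A); exclusion at six missed classes (10.A, 11.1).

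**Assumptions.** All controls return; there is no true effect averaged over all dancers who start; a fraction w of dancers is lost; leavers' mean change in sway is d SD worse than stayers'; changes are normal with equal SD; testing is two-sided at 5%.

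**Step 1: who is lost under which rule.** Ten to 12 weeks gives 2 × 10 = 20 to 2 × 12 = 24 classes. A dancer who stops with six or more classes left reaches six absences and is excluded whatever 10.B says. A dancer with no earlier absences who stops with five or fewer left is not caught by the attendance rule. Quitting for the last two weeks, for example, misses 2 × 2 = 4 classes. The withdrawal wording therefore adds loss mainly among these late leavers.

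**Step 2: bias from both rules together.** If the mean over all starters is zero, the stayers' mean is too favourable by w × d.
- w = 20%, d = 0.5: 0.20 × 0.5 = 0.10 SD.
- w = 30%, d = 0.8: 0.30 × 0.8 = 0.24 SD.
- d = 0: no bias, whatever w is.

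**Step 3: chance of a false result favouring ballet.** The normal approximation is P(Z > 1.96 − bias/SE), with SE = √(1/dancers remaining + 1/20).

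| Loss, gap | Dancers left | SE | bias/SE | Normal approximation | Simulated Mann-Whitney |
|---|---|---|---|---|---|
| none | 20 | 0.316 | 0 | 2.5% | 2.6% |
| 20%, 0.5 SD | 16 | 0.335 | 0.30 | 4.8% | about 4% |
| 30%, 0.8 SD | 14 | 0.348 | 0.69 | 10.2% | about 9% |

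The simulation used 20,000 runs per row with normal changes. With the same losses but d = 0, the two-sided rejection rate stayed between 4% and 5%.

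**Step 4: share due to the withdrawal wording alone.** If leaving times are evenly spread (an assumption), the late leavers of Step 1 are 5/20 = 25% of leavers, or 5/24 = 21%. Taking 25%:
- 0.25 × 20% = 5% added loss; 0.05 × 0.5 = 0.025 SD.
- 0.25 × 30% = 7.5% added loss; 0.075 × 0.8 = 0.06 SD.

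The chance of a false favourable result is then about 3% and 4%.

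**The case against.** The strongest reply is that the rule is triggered by withdrawal from the study, not from class. Not recalling people who withdraw is ordinary and should stay. The sentence before it can be read as two separate freedoms, and the email wording in 10.C supports that reading. This stands. A reader might infer that the plan forbids post-testing of anyone who stops class, but it does not say so; it is silent or ambiguous. What survives is that no status, and no instruction to invite, exists for the class-only leaver.

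Three other tempting inferences go further than the documents:

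- *Controls face no comparable loss.* The withdrawal sentence covers both groups, and controls may also leave. Only the class-quitting route and the attendance rule are one-sided.
- *The SF-36 results are biased too.* The sentence names balance testing only, and no SF-36 test is planned. Loss of SF-36 forms is probable, since they are completed at post-testing, but it is an inference.
- *The whole attrition bias comes from this sentence.* Dancers who stop with six or more classes left already meet the attendance exclusion.

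The direction of bias is also not established. Some leaving, such as for transport, has no evident link to balance, and section 13 describes the class as gentle.

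**Conclusion.** The point holds in this limited form. The plan does not distinguish stopping class from leaving the study. Together with the attendance exclusion, it leads to a dancer group made up of completers, while controls face neither of those two routes of loss.

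The combined bias is 0.10 to 0.24 SD under the two scenarios shown, and zero if leaving is unrelated to change in sway. The withdrawal wording alone accounts for roughly 0.03 to 0.06 SD. These figures rest on assumed loss, an assumed gap between leavers and stayers, full return of controls and, for the second range, evenly spread leaving times. The documents supply none of these. The matter should be corrected because the remedy is cheap and the missing data cannot be collected later.

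**What to change.** 1. In 10.B, define two statuses. A participant who *stops ballet classes* stays in the study and is invited to the scheduled end-of-semester balance test and SF-36, free to decline. A participant *withdraws from the study* only by saying so, and is then not contacted further.
2. In 10.A and 11.1, stop using six or more missed classes to remove dancers from post-testing or from the main comparison. Without this, step 1 recovers mainly late leavers.
3. In 11.3, analyse all enrolled dancers with a post-test as the ballet group, use the attendance-based set as a sensitivity analysis, and report losses and their reasons by group.

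The cost is a minor amendment with matching consent wording, one test session of about 15 minutes (the time given in 11.2) for each class-leaver who agrees, and possibly a smaller observed effect. None of this removes the selection bias that comes from participants choosing their own group.

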11.1 Beginning Ballet Class Information

One-hour ballet classes will be held twice per week in one of the two dance studios or in the dance theater at Skidmore College. [name] '20 will serve as the lead teacher for each dance class from February 4th-April 26th. Other Skidmore students may serve as lead teacher in future semesters as determined by the PI and/or [name]. Each week the participants will partake in 120 minutes of ballet dance training, starting with warm-up exercises at the barre and then working towards learning combinations in the center. Participants may take short breaks to get a drink or use the bathroom as they need. Chairs will be set up in the dance studio or dance theater so individuals can rest

or take a break if they wish. They will learn the basic positions and combinations used in ballet, including: Plié, Tendu, Degagé, Rond de Jambe, Frappé, Chassé, Sauté, Pas de Bourrée, Glissade, and Révérence. Additional ballet movements and patterns may be employed as well. If a participant chooses not to dance for the full duration of a given class period, an assistant teacher may assist them out of the studio to wait comfortably in the lobby of the dance center, dance gym or sports center until the class ends and their transportation arrives if needed. They may also rejoin the class at any time, should they choose. Attendance will be taken at the start of each class to ensure that participants do not miss six or more classes in line with our exclusion criteria. Attendance will be documented in a password-protected electronic file through the participants' number IDs alongside the initials of their first and last name to maintain anonymity of the attendance document. Only [name], [name], and the lead teacher will have access to the attendance roster each semester.

Prior to any participation in the ballet classes and to pre-testing, an intake form will be completed by each participant (please see intake form below). Additionally, participants will complete a quality of life (QOL) survey at pre- and post-testing to gather quantitative data regarding their quality of life using the 36-item Short-Form Health Survey (SF-36; see attached), which is a widely-used tool for assessing QOL in elderly people (16). The experimental group will also complete an exit survey at post-testing that will specifically ask about their reactions to the ballet class intervention both quantitatively with 1-5 scales and qualitatively (see attached).

The only people who will have full access to the completed intake, SF-36, and exit survey forms will be [name] and [name] PT, DPT. The names of the participants will be removed from the documents and replaced with the participant ID numbers prior to any data analysis to ensure confidentiality. These files will be kept in a locked filing cabinet in office 228 of the Williamson Sports Center at all times and will not be removed from the office.

Skidmore students acting as assistant teachers for the ballet classes will receive training packets with all necessary information about the logistics of the class and suggestions on how to assist during the classes. The packet will discuss appropriate interactions and confidentiality during the class.

Additionally, lead teacher will work closely with [name] PT, DPT to address teaching strategies and to create lesson plans modeled after [name] course DA101: The Dance Experience. [name] will also be consulting with the lead teacher throughout the process and assisting in modifying lesson plans as appropriate for older adults. The lead teacher may choose to complete an independent study to receive academic credit for their work teaching the beginning ballet classes as determined by the student and [name].

*Please note: Student teachers and assistant teachers are not assisting with data collection and analysis and will not have access to any data collected for the purposes of research.

11.2 Data Collection

Data collection will take place at the dance conference room (Williamson Sports Center), the Human Performance Teaching Lab (Sports 101, Williamson Sports Center), multipurpose room (Williamson Sports Center), the intramural gym (Williamson Sports Center), or at the Prestwick Chase facility or the Saratoga Senior Center (if requested by an activities director) prior to the start of the ballet classes each semester with post-testing to be completed the week of, or following, the final ballet class of the semester. Tests of postural stability will be verbally explained/instructed to create clear expectations for the test and to help decrease any fear or anxiety surrounding the process.

Data collection will be conducted by [name] '19 with help from [name] as needed. Following the Spring 2019 semester, [name] will lead data collection and/or find another Skidmore student to help with data collection who is trained with this protocol. [name]

[name] will be contacted as needed to ensure the proper functioning of the data collection system/protocol. [name] has already received training in the data collection procedure from [name] and [name] from a prior research investigation examining postural stability in novice collegiate dancers (IRB 1712-683). Once calibrated, the use of balance boards to collect data on postural stability requires very little technical skill, and therefore it is appropriate for a trained student researcher to lead this process. Any additional student data collectors present will only be there to assist and guard the participants from falling. Student data collectors will be trained in all procedures and techniques directly by the PI or supervising faculty members prior to any data collection and must be able to demonstrate competency in testing prior to administering any tests on participants.

Both the pre and post data collection will take approximately 15 minutes per participant at each testing session. Participants will receive instructions prior to each trial of 30 seconds with at least one research assistant spotting the participant should they lose their balance. Participants will be asked to stay in a static standing position for 3 trials of 30 seconds while standing on a Wii board in four of the following conditions : 1) bilateral stance with eyes open, 2) bilateral stance with eyes closed, 3) unilateral stance on the right limb 4) unilateral stance on the left limb. Participants will be given a 15 seconds rest period between each trial and will be told they may stop and rest at any moment during the testing process.

11.3 Data Analysis

Five measures of postural stability were examined in this study: the area the CoP traveled through during each 30-second trial, the CoP displacement in the x- and y-planes during each trial, and the absolute value of the average speed of the CoP in the x- and y-planes through each trial. Non-parametric Wilcoxon signed ranks tests were used to compare these values at baseline and post-testing within each group, while non-parametric Mann Whitney U tests were used to compare the delta (post minus pre) values between groups for EO and EC trials.

12. Consent:

Participants will sign an Informed Consent must prior to beginning of any testing. Please see attached informed consent for details.

13. Risks and Debriefing:

The postural stability data collection offers minimal risk to participants. Fatigue and falls have been shown to be minimal in prior research (see background information on postural stability references) in older adults. To ensure no risk to participants, participants will repeatedly be reminded they may rest or stop at any moment, without penalty of any kind. As well, one 'spotter' will be present during all data collection trials to assist participants should they lose their balance.

The dance movements performed in the intervention sessions carry a minimal risk of injury. Ballet movements presented in the class will likely be outside of typical movement patterns and therefore hold some inherent risk, including slips, falls and muscle strains and sprains. To combat the likelihood of injury during the class, participants will be thoroughly instructed on the movement, technique, and expectations for each combination. The ballet class will be gentle with little to no aerobic activities, making this appropriate for all participants meeting our inclusion criteria. Additionally, while the class will be primarily instructed by the lead teacher, additional Skidmore students will be present to help decrease the risk of injury during the dance class. This way, each participant has additional support throughout the class time as needed.

If a serious injury occurs, the Skidmore Campus Safety will be called and/or 911 depending on the severity of the injury. If an injury occurs during testing off-campus, 911 will be called to appropriately treat the participant for any injury sustained.

Participants will not be formally debriefed following the study as no deception is being used in our methods. All aspects of the study and its intentions will be disclosed to the participants prior to their involvement through the informed consent form. Participants will not be told their individual scores on each test as not to bias the data.

There are minimal psychological risks of participating in this study. Participants may feel frustrated at times during the dance class if they are not able to perform the movement as directed by the instructor and may feel discouraged if they are unable to perform a test during data collection. There is also a risk of low self-esteem if the participant is comparing their dance abilities to others in the class. The instructors and/or researchers will make all efforts to encourage participants throughout this experience to enjoy the process regardless of their outcomes; to do their best and focus on their own personal artistic exploration throughout their time in the class. Furthermore, all assistant teachers and researchers will receive information from PI [name] and [name] discussing pedagogical practice and motivation in the dance studio. All movement combinations given to the participants in the dance studio will be created and/or screened by the lead teacher or PI [name] or [name] based on [name] work to assure that the movement structure is appropriate for the participants' physical abilities. [name] has over 20 years of experience teaching dance to students of all ages/abilities in addition to her doctorate in Physical Therapy with work in the acute care, inpatient and outpatient rehabilitation fields.

14. Privacy and Storage of Data:

The records of this study will be kept private. In any sort of report that is published or presentation that is given, we will not include any information that will make it possible to identify any of the participants involved.

Any data that was initially collected in hard copy (consent forms, intake forms, SF-36 forms, exit surveys) will be kept in a locked filing cabinet in office 228 of the Williamson Sports Center. [name] will possess the key to the filing cabinet, and only [name] and [name] will be able to view these documents. Data collected during balance testing will be automatically recorded in a password-protected Microsoft Excel spreadsheet accessible to both [name] and [name].

